A nationwide, parallel-group randomized controlled superiority trial is conducted comparing an adapted MBSR + SAU (intervention) with SOM + SAU (control). The intervention is an interactive adapted videoconferencing MBSR group-training. The training consists of eight 1,5 hour sessions twice a week during 4 weeks. The sessions will be held via interactive videoconferencing. Participants in the control condition will have the possibility to use a self-help daily mindfulness exercise (30 minutes) on a YouTube channel. In total the participants will receive 24 mindfulness and compassion exercises in 4 weeks. Treatment allocation is a 1:1 ratio. Assessments will be conducted at baseline (T0), mid-treatment (T1), and at 1 (T2), 4 (T3) and 7 (T4) months follow-up. Participants randomized to the SOM + SAU condition will be able to participate in an adapted MBSR intervention after they completed the study (7 months).

Randomization

Random assignment to adapted MBSR + SAU or SOM + SAU is electronically conducted by CastorEDC. Randomization is stratified by setting (3 levels: hospital, nursing home, other), prior mindfulness training (yes/no), and profession (3 levels: physician, nurse, other). Block randomization with predefined blocks are used (2 or 4) in order to ensure balanced groups. Diagnostic research assessors conducting clinical interviews were blinded to the treatment allocation.

Sample size

Based on Lai et al.[1], high post-exposure levels of depression, anxiety, insomnia and distress are expected (in 50-70% of healthcare workers). So far, no data exist on changes of these levels of distress in healthcare workers in the COVID-19 pandemic due to interventions.

Therefore, we aim to detect an effect-size of 0.4 ($\alpha=0.05$; $\beta=0.20$; two-tailed). When using t-tests, a sample size of 200 (100 in each arm) is needed. This will suffice to reveal a clinically relevant difference of 5 points on the PHQ-SADS[8] (scale of sum-score 0-78). To overcome attrition, we will increase the size of our groups with 10%. Thus, a total of 220 participants (110 in each group) will be included in this randomized controlled study.

Framework

Both primary and secondary outcomes will be assessed for superiority of an adapted MBSR + SAU above SOM + SAU.

Statistical interim analyses and stopping guidance

Not applicable

Timing of final analysis

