All outcomes will be analyzed collectively after the T4 measurement and the SCID5 interviews have taken place in the last participants (anticipated being June 2022).

Timing of outcome assessments

At baseline participants complete the questionnaires used for our primary/secondary outcomes. The same questionnaire are send after 1 month (post-intervention), and after 4 and 7 months. To measure possible mediators three questionnaires are used at mid-treatment (2 weeks after start of

the intervention). At 7 months the occurrence of psychopathology is measured by the Structured Clinical Interview for DSM-5 (SCID5).

Section 4: Statistical Principles

Confidence intervals and P values

Level of statistical significance

All applicable statistical tests will be 2-sided and will be performed using a 5% significance level.

Description and rationale for any adjustment for multiplicity

Not applicable

Confidence intervals to be reported

All confidence intervals presented will be 95% and two-sided.

Adherence and protocol deviations

Definition of adherence to the intervention and how this is assessed

Adherence implies that participants attended ≥ 4 sessions in the adapted MBSR + SAU group. The MBSR trainer will keep an attendance register.

Participants in the SOM + SAU group will be asked at timepoint T1 and T2 how often they did a mindfulness exercise in the last two weeks.

Analysis populations

All analyses will be conducted in SPSS version 25 and will be performed as intention-to-treat (ITT). The intention-to-treat population will include all randomized patients, according to the treatment they were randomized to receive. Secondary, per protocol analyses will be conducted.

Section 5: Trial Population

Screening data

Potential participants fill out an online registration form expressing their interest for the study. Next, a screening interview by telephone is planned. Study information will be given and in- and exclusion criteria will be checked during this interview. All screened potential participants and their eligibility will be registered.

Eligibility

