The Trimbos/iMTA questionnaire for Costs associated with Psychiatric illness (TiC-P) [25] will be used to collect information on direct healthcare use and paid and informal work-related productivity losses at 7 months. The EuroQol-5D-3L (EQ-5D) will be used to measure health-related quality of life.

COVID-19 related questions and mindfulness practice questions will be asked.

Analysis methods

Treatment effects at T4

Primary analyses will be performed on the intention-to-treat (ITT) sample. ANCOVA will be used to examine the main effect (PHQ-SADS) of the intervention at T4. Roughly, every month during approximately one year a group will start with the intervention (cohort). Due to the expected differences in these groups, cohort effects will be added. Therefore, a Linear Mixed Effect Model will be used for the analyses. Group (adapted MBSR + SAU / SOM + SAU) will be added as fixed effects, while controlling for baseline levels. A random effect for cohort will be added, and if applicable as a fixed effect. Cohen's *d* effect size will be calculated by dividing the adjusted group difference at T4 by the pooled standard deviation at T0. [26]

Difference in occurrence of psychopathology (present/absent) between adapted MBSR + SAU and SOM + SAU assessed by SCID-5 interview at T4 will be tested with Chi-square test.

Course to treatment effect at T4

The course of treatment effects from baseline to T4 for both primary and secondary outcomes (post-traumatic stress symptoms, insomnia, alcohol use, post-traumatic growth, positive mental health) at

T2, T3, and T4 will be evaluated with Linear Mixed Effects Models. Time, group (adapted MBSR + SAU / SOM + SAU) and their interaction will be added as fixed effects, while controlling for baseline levels. A random effect for participant and cohort (random slope and intercept) will be added. Heterogeneous first-order autoregressive (ARH(1)) covariance structure will be used, which assumes that measurements closer in time are more strongly related to each other. Restricted maximum likelihood will be used as estimation method to handle missing data. Cohen's *d* effects size will be calculated by dividing the adjusted group difference between the pooled means (T2, T3, T4) by the pooled standard deviations at T0.[26]

Moderation of the effect

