Moderation will be examined by adding the potential moderator and its interaction with group to the model. Separate models will be run for each possible moderator. The following possible moderators will be used: gender, age, work setting, profession, prior mindfulness training, adherence, baseline depressive, anxiety and somatic symptoms, and baseline perseverative thinking, mindfulness and self-compassion.

Mediation of the effect

Mediation analysis will be performed on per-protocol sample, using the multiple mediation model by Preacher & Hayes.[27] We will examine whether T0 to T1 change in potential mediators (mindfulness skills, self-compassion, and perseverative negative thinking) mediated T0 to T2 change in depressive, anxiety and somatic symptoms, post-traumatic stress symptoms, insomnia, post-traumatic growth and positive mental health.

Any adjustment for covariates

See above

Methods used for assumptions to be checked for statistical methods

Assumptions of normality will be checked and, in case of lack of normality, bootstrapping will be used to account for this problem.

Any planned sensitivity analyses for each outcome

Sensitivity analyses will be conducted by performing the primary and secondary analyses in the per-protocol (PP) sample. The per-protocol analysis set consists of subjects who have a minimum exposure of 4 MBSR sessions (intervention group (adapted MBSR + SAU)). Further sensitivity analysis will be performed depending on possible patterns in missing values and when relevant disbalance in covariates will be observed.

Any planned subgroup analyses for each outcome

Moderation will be examined by adding the potential moderator and its interaction with group to the model. Separate models will be run for each possible moderator. The following possible moderators

will be used: gender, age, profession, work setting, prior mindfulness training, baseline levels of depressive, anxiety and somatic symptoms.

Missing data

No imputation will be needed for baseline measures, because participants were only randomized if T0 was completed. The questionnaires will be filled in an online platform (CastorEDC), in which it is required to fill in an item before continuing to the next item. Therefore, we expect a low number of missing data.

Additional analysis

None

Harms

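### The SCID-5 chi-square test omits the cohort effect that the plan expects and models for the questionnaires, so its 5% level is not secured; the mediation analysis has the same gap to a lesser degree

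*SAP*

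**What the plan says.** Section 3 (Trial design) describes adapted MBSR as a group training by videoconference. Controls use self-help exercises on a video channel, without groups.

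Section 6 (Treatment effects at T4) says that a group starts the intervention roughly monthly for about a year, and calls this a cohort. It continues: "Due to the expected differences in these groups, cohort effects will be added". On that ground the T4 analysis of PHQ-SADS becomes a linear mixed model with a random cohort effect, or a fixed one if applicable. The models for the course of the questionnaire outcomes carry random participant and cohort effects. Moderators are added to the existing model and so keep the term.

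Two analyses do not carry it:

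- **II.1, SCID-5.** The difference in psychopathology "assessed by SCID-5 interview at T4 will be tested with Chi-square test".
- **II.5, mediation.** "Mediation analysis will be performed on per-protocol sample, using the multiple mediation model", with no mention of cohort.

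Section 4 sets the level: "All applicable statistical tests will be 2-sided and will be performed using a 5% significance level". It makes no adjustment for multiplicity.

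**The concern.** A chi-square test assumes independent participants and cannot carry a cohort term. The plan states a premise (cohorts differ), acts on it for the questionnaires, and then names a test for SCID-5 that ignores it. Nothing later repairs this. The specified sensitivity analysis repeats the analyses in the per-protocol sample, further ones depend on missing-value patterns or covariate imbalance, and additional analyses are given as none. The bootstrap in Section 6 is there for non-normality, and resampling individuals would not restore the dependence between them.

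II.1 is the first secondary question and the only outcome for which the SAP states blinded assessors (Section 3, Randomization). A positive result could be read as support for a self-reported primary outcome, so its error rate should be known.

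**Working it through.** **The plan's own figure.** For d = 0.4, two-sided 5% and 80% power, the normal formula gives 2 × (1.96 + 0.842)² / 0.4² = 98.1, so 99 per arm. The exact t-test gives 99.1, so 100. This matches "a sample size of 200 (100 in each arm) is needed", and 200 × 1.10 = 220 matches "a total of 220 participants (110 in each group) will be included in this randomized controlled study". The sample size is not in dispute; it supplies the 110 per arm used below.

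**Inputs**

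- From the SAP: 110 per arm; about 12 groups (monthly for about a year), so m = 110/12 = 9.2 MBSR participants per group; two-sided 5%.
- Assumed: ICC of 0.02, 0.05 or 0.10 (the SAP gives none), and diagnosis rates of 15 to 50% in the simulations.

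**Reading A: correlation within MBSR training groups only, controls independent**

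- Design effect in the MBSR arm = 1 + (m − 1) × ICC.
- Variance ratio of the arm comparison, true to assumed = (1 + design effect)/2.
- True type I error = 2 × [1 − Φ(1.96/√ratio)].

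| ICC | Design effect | Variance ratio | Type I error, formula | Type I error, simulated chi-square (12 groups of 9) |
|---|---|---|---|---|
| 0.02 | 1.163 | 1.082 | 6.0% | 5.9–6.0% |
| 0.05 | 1.408 | 1.204 | 7.4% | 7.2–7.6% |
| 0.10 | 1.817 | 1.408 | 9.9% | 9.6–9.9% |

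With no correlation the simulation returns 4.8 to 5.1%, as it should. The assumed standard error is too small by 1 − 1/√ratio, which is 4%, 9% and 16%. With 10 groups instead of 12 the formula gives 6.2%, 8.0% and about 11%; with 14 groups it gives 5.8%, 7.0% and 9.1%.

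**Reading B: cohort is a calendar wave shared equally by both arms, with no training-group effect**

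The wave cancels from the arm difference, so the variance ratio is about 1 − ICC, and the chi-square test overstates the variance. Simulated type I error is 4.6 to 5.2% at ICC 0.02, 4.2 to 4.7% at 0.05 and 3.9 to 4.3% at 0.10.

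**Mediation, under reading A**

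The simulation used one mediator, a percentile bootstrap of individuals, 12 groups of 9, and group effects on mediator and outcome that were perfectly correlated. False-positive rates for the indirect effect at ICC 0, 0.05 and 0.10 were:

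- no treatment-to-mediator effect: 5.9%, 7.4% and 10.5%;
- no mediator-to-outcome effect: 4.6%, 6.3% and 10.4%.

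In the second case part of the excess is confounding by group. The shared group effect gives a covariance equal to the ICC in one of the two arms, so the pooled slope is about ICC/2 = 0.05 at ICC 0.10 when the true slope is zero.

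**The case against.** A reader might infer that the p-values are simply too small. The SAP does not support that as a fact. It expects cohorts to differ but does not say that the differences are confined to the MBSR arm. Its option of a fixed cohort effect beside the arm effect points the other way: if only MBSR participants had cohorts, the cohort indicators would sum to the arm indicator and the arm effect could not be estimated. So controls may well be assigned to cohorts. Randomization in blocks of 2 or 4 would also roughly balance the arms over calendar time. Reading B then applies at least in part.

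A mixture shrinks the error. With groups of 9, the ratio is 1 − (shared ICC) + 4 × (training-group ICC). Splitting a total of 0.05 evenly gives 1 − 0.025 + 0.100 = 1.075 and a type I error of about 5.9%. Splitting 0.10 evenly gives 1.15 and about 6.8%. If the shared part were four times the training-group part, the two would cancel.

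This objection stands as to direction and size. It does not justify the test: the level then depends on an unstated balance between two effects that the other models address through a cohort term. Reading A also remains plausible, because MBSR is taught in groups and the SAP defines a cohort as a group starting the intervention.

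On mediation, the objection is stronger. The point rests only on the absence of a cohort term, and the SAP states no p-value there, so the harm is mainly an interval that may be too narrow.

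**Conclusion.** The SCID-5 test is at odds with the plan's own premise. If correlation sits within MBSR training groups, the nominal 5% test runs at about 6% to 10% for assumed ICCs of 0.02 to 0.10. If cohort is purely a shared wave, it runs at about 4 to 4.7% for ICCs of 0.05 to 0.10 and close to nominal at 0.02. The level is off on either pure reading once the ICC is appreciable, but the direction cannot be settled from the SAP. The figures rest on an ICC that the SAP does not give and on about 12 groups of about 9.

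The mediation gap is real but lesser. The primary analysis already carries a cohort effect and is not affected. Severity is minor to moderate.

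**What to change.** - **Define cohort.** State whether controls are assigned to cohorts, and whether each cohort holds one MBSR training group or several.
- **II.1.** Make the test a logistic mixed model with the primary model's cohort effect and training-group clustering in the MBSR arm. Alternatively, use GEE with a small-sample correction. If controls have no cohort, treat each control as an own cluster. Keep the chi-square as descriptive.
- **II.5, lesser.** Obtain the intervals for the indirect effects by resampling whole MBSR training groups and individual controls. This addresses the width of the intervals but not confounding by group, which would need a group term in the equations.

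The cost is a change of SAP wording, some more code, and slightly wider intervals if reading A holds. No new data are needed, since the primary model already requires cohort membership. SPSS 25 is the only package the SAP names, so confirm that it can do the small-sample correction and the group-level bootstrap, or name another.

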Consequently, MBSR is a potentially useful intervention to prevent psychopathological sequela of the high-stress situations that healthcare workers went through in the current COVID-19 pandemic. The aim of this study is to examine the effectiveness of an adapted MBSR intervention delivered via videoconferencing to reduce psychological distress in COVID-19 healthcare professionals.

Objectives

Primary research question:

- I. Is an adapted videoconferencing MBSR intervention + support as usual (SAU) superior to a standalone online mindfulness intervention (SOM) + SAU in terms of reducing psychological distress (measured by a compound measure of depressive, anxiety, and somatic symptoms) at 6 months after completing the intervention (= 7 months follow-up)?

Secondary research questions:

Additional outcome measures

- II.1 Is there less psychiatric psychopathology diagnosed by clinical interviews after adapted MBSR + SAU compared to SOM + SAU at 7 months follow-up?
- II.2. Is an adapted MBSR + SAU more effective than SOM + SAU in reducing psychological distress (depressive, anxiety, and somatic symptoms) and post-traumatic stress symptoms, insomnia and alcohol use over the course of 7 months after baseline?
- II.3. Is an adapted MBSR + SAU more effective than SOM + SAU in improving post-traumatic growth and positive mental health over the course of 7 months after baseline?

Moderation of the effect

II.4 Is the effect of an adapted MBSR to reduce psychological distress moderated by gender, age, work setting, profession, prior mindfulness training, adherence, baseline depressive, anxiety and somatic symptoms, and baseline perseverative thinking, mindfulness and self-compassion?

Mediation of the effect

II.5 Is the effect of and adapted MBSR and SOM + SAU to reduce psychological distress mediated by a decrease of perseverative thinking, and an increase in mindfulness skills and self-compassion?

Section 3: Study Methods

Trial design

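### Adherence is planned as a treatment-effect moderator, but it has no common definition across arms and arises after randomization; as defined, its interaction with group cannot be estimated

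*SAP*

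**What the plan says.** Research question II.4 (Objectives) asks whether the effect on distress is "moderated by gender, age, work setting, profession, prior mindfulness training, adherence" and by a set of baseline scores. Section 6, Moderation of the effect, repeats that list, which ends with "prior mindfulness training, adherence, baseline depressive, anxiety and somatic symptoms, and baseline perseverative thinking, mindfulness and self-compassion", and fixes the method: "Moderation will be examined by adding the potential moderator and its interaction with group to the model", with one model per moderator.

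Adherence is defined once, in Section 4 under Adherence and protocol deviations: "Adherence implies that participants attended ≥ 4 sessions in the adapted MBSR + SAU group", taken from the trainer's register. For the other arm, the same heading says only that SOM participants are "asked at timepoint T1 and T2 how often they did a mindfulness exercise" over the preceding two weeks. It gives no cut-off, no rule for combining T1 with T2, and no statement that this is the SOM value of the moderator. The SOM arm has no sessions to attend; Section 3 describes its exposure as exercises to be done alone: "In total the participants will receive 24 mindfulness and compassion exercises in 4 weeks". The per-protocol set in Section 6 likewise has a criterion for MBSR only.

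The planned subgroup analyses in Section 6 repeat the moderation rule with a shorter list: "gender, age, profession, work setting, prior mindfulness training, baseline levels of depressive, anxiety and somatic symptoms". Adherence is not on it, nor are baseline perseverative thinking, mindfulness and self-compassion.

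**The concern.** A moderator analysis asks whether the randomized contrast differs between kinds of participant. The moderator must therefore mean the same thing in both arms and should be fixed before treatment can influence it. Adherence as defined here meets neither condition. It is a property of the MBSR arm, and it comes about during the four weeks of training.

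Two things can go wrong. If the analyst applies the written definition, the interaction that II.4 asks for does not exist as a separate term. Whatever adherence coefficient the software returns is a non-randomized comparison of MBSR attenders with MBSR non-attenders. If the analyst puts SOM practice frequency in its place, a coefficient appears, but it can differ from zero when the treatment does nothing to anyone. That happens if attending sessions and practising at home relate differently to prognosis. Such a result could be reported as showing that MBSR works better in those who adhere.

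**Working it through.** **Inputs from the SAP.** Section 3 gives 1:1 allocation and 110 per arm. The size reproduces: a two-sided t-test with d = 0.4, alpha 0.05 and power 0.80 needs 99.08, so 100, per arm, and 200 × 1.10 = 220. The point below does not depend on this figure.

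**Step 1: can the prescribed model be fitted?** Let G = 1 for MBSR and 0 for SOM, and A = 1 if adherent. The columns are 1, G, A and G×A. Suppose some MBSR participants fall on each side of 4 sessions.

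| Value of A in the SOM arm | Consequence | Rank |
|---|---|---|
| All 0 | G×A = A | 3 of 4 |
| All 1 | G×A = A + G − 1 | 3 of 4 |
| Missing | MBSR only: G = 1 and G×A = A | 2 of 4 |
| Dichotomized practice frequency | No identity holds | 4 of 4 |

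The numerical ranks of the design matrix agree. Adding a baseline covariate adds one to both the rank and the number of columns, so the deficiency remains. The first three rows are algebra and hold for any attendance rate strictly between 0 and 100%.

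**Step 2: what does the estimable coding measure?** Assume no treatment effect in anyone and a residual SD of 1. Assume that 80% of MBSR participants attend at least 4 sessions, and that a latent normal propensity to attend has correlation ρ with a better (lower) T4 score. Assume also that 30%, 50% or 70% of SOM participants are classed as adherent and that SOM practice is unrelated to outcome. The SAP supplies none of these values.

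The expected attender minus non-attender difference in MBSR is −ρ·φ(z)/[p(1 − p)]. With p = 0.8, φ(z) = 0.280, and 0.280/0.16 = 1.75. The expected difference in SOM is 0, so the false interaction is −1.75ρ: 0, −0.175, −0.35 and −0.525 SD for ρ = 0, 0.1, 0.2 and 0.3.

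With 50% of SOM classed as adherent, the cells are 88, 22, 55 and 55. The standard error is about √(1/88 + 1/22 + 1/55 + 1/55) = √0.0932 = 0.305. For ρ = 0.2, 0.35/0.305 = 1.15, and the chance of exceeding 1.96 in absolute value is about 21%.

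Simulation (5000 trials per scenario) agrees:

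| ρ in MBSR | ρ in SOM | Mean false interaction (SD) | Rejection at 5%, over the three practice shares |
|---|---|---|---|
| 0 | 0 | about 0 | 4.6–5.0% |
| 0.1 | 0 | −0.18 | 8.1–9.2% |
| 0.2 | 0 | −0.35 | 19.2–21.7% |
| 0.3 | 0 | −0.53 | 37.0–41.0% |
| 0.2 | 0.2 | not tabulated | 4.6–5.0% |

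The last row shows that the inflation comes from the asymmetry between the two measures.

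**Step 3: the two lists in Section 6.** The same rule is stated twice. The list under Moderation of the effect contains adherence and three baseline process measures that the subgroup list lacks. The SAP does not say whether the shorter list is a deliberate subset.

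**The case against.** The best reply is that the SOM practice question stands under the same heading as the MBSR criterion, so it is naturally read as the SOM adherence measure with its scoring left open. On that reading the model has full rank. This is fair, and it limits the claim of non-identification to the literal definition. It does not rescue the analysis: the two arms would be scored on different behaviours by different instruments, and the result would still be a comparison of self-selected groups.

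A second reply is that Section 6 also announces that "COVID-19 related questions and mindfulness practice questions will be asked", without restricting this to one arm, so a common measure may exist. The SAP neither defines these questions nor ties them to adherence or moderation. A common practice measure would still be recorded after randomization.

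Third, the simulated rates rest on assumed inputs and on prognosis mattering in one arm only. That is correct. They show that a false interaction is possible and how it scales; they do not predict its size in this trial.

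Fourth, the SAP never calls adherence a baseline variable, and this is one moderator among many in a secondary question. Both are true. The first does not make the interaction interpretable as effect modification. The second limits the weight of the point but does not remove it.

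**Conclusion.** The point holds. As written, the moderation rule cannot answer II.4 for adherence. Under the literal definition the interaction is not identified, whatever the attendance rate, as long as some MBSR participants attend 4 or more sessions and some do not. Under an arm-specific reading it is estimable, but it is a non-randomized contrast between unlike measures. With no treatment effect and the stated assumptions, it can be wrong by roughly 0.2 to 0.5 SD for correlations of 0.1 to 0.3, with rejection rates of about 8% to 41%; with symmetric prognosis there is no inflation.

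The two moderator lists in Section 6 also disagree. Neither matter touches the primary intention-to-treat comparison or the sample size. It should be corrected before analysis, but it does not threaten the trial's main conclusion.

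**What to change.** Remove adherence from II.4 and from the moderator list in Section 6; the list under planned subgroup analyses already omits it. Use a single list of baseline moderators in both places in Section 6, and state whether baseline perseverative thinking, mindfulness and self-compassion belong to it. Report session attendance within the MBSR arm as a descriptive association with outcome, labelled as non-causal.

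This changes SAP wording only. It needs no new data, and the primary analysis stays as it is.

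### Mediation (question II.5) is planned only on a per-protocol set that selects the MBSR arm on attendance; no ITT mediation analysis is specified

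*SAP*

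**What the plan says.** SAP Section 6, *Mediation of the effect*: "Mediation analysis will be performed on per-protocol sample". The mediator side is fixed in the same paragraph, "We will examine whether T0 to T1 change in potential mediators", and is related to T0-T2 change in the outcomes. No second analysis set is named and no reason is given for the choice.

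The set is defined under the planned sensitivity analyses in Section 6: "The per-protocol analysis set consists of subjects who have a minimum exposure of 4 MBSR sessions (intervention group (adapted MBSR + SAU". No criterion is given for SOM + SAU, although Section 4 (*Adherence and protocol deviations*) has those participants report practice frequency at T1 and T2.

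Section 4, *Analysis populations*, sets the general rule: "All analyses will be conducted in SPSS version 25 and will be performed as intention-to-treat (ITT", followed by "Secondary, per protocol analyses will be conducted". For the primary and secondary analyses, Section 6 uses the per-protocol set only as a sensitivity re-run.

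Three design facts matter here. Section 3 says of the course: "The training consists of eight 1,5 hour sessions twice a week during 4 weeks". Control participants "will have the possibility to use a self-help daily mindfulness exercise". On timing, Section 3 states: "To measure possible mediators three questionnaires are used at mid-treatment", that is, two weeks after the start.

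**The concern.** Mediation is the one analysis for which per-protocol is the only named set, which reverses the SAP's own order of ITT first and per-protocol second. Because the criterion applies to one arm, MBSR attenders are compared with an unselected control arm. If attenders would have changed differently anyway, that difference enters the group-to-mediator path and the total effect, and so the indirect effect.

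If attenders have the better course, mediation can be declared although MBSR moved nothing. If they have the worse course, the error favours SOM. As written, no planned mediation analysis would reveal either.

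**Working it through.** **1. The texts side by side.** The general rule in Section 4 is ITT; the specific rule in Section 6 is per-protocol. A specific rule normally prevails, so an analyst following the SAP would run mediation on the per-protocol set alone.

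**2. Who is in the set.** Read literally, the definition admits only people with MBSR sessions, which would leave no control arm. The natural reading keeps every SOM participant, since their exercises were optional. Selection then acts on the MBSR arm only.

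**3. Timing.** Two sessions a week for two weeks gives 2 × 2 = 4 of 8 sessions held by about T1. Anyone who missed one of these can reach four only after the mediator has been measured. Membership can therefore depend on how the mediator changed early on.

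**4. The SAP's own figure.** The SAP gives no figure for mediation. Its sample size is reproduced: with d = 0.4, two-sided alpha 0.05 and power 0.80, the normal formula gives 99 per arm and the t-test 99.1, so 100 per arm as stated. Taking 10% off the 110 randomized per arm leaves 110 × 0.9 = 99.

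**5. Size of the selection bias (assumed inputs).** The SAP gives neither the adherent proportion p nor the correlation r between attendance and change not caused by treatment. I take p = 0.75 and 0.85, so 99 × p is about 74 or 84 MBSR participants against 99 SOM. For a normal attendance tendency cut at z, the attenders' mean change is shifted by r·φ(z)/p SD:

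- p = 0.75: 0.042, 0.085, 0.127 for r = 0.1, 0.2, 0.3
- p = 0.85: 0.027, 0.055, 0.082

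With three mediators correlated 0.5 with each other and each 0.5 with outcome change, each slope is 0.5/(1 + 2 × 0.5) = 0.25, and the slopes sum to 0.75. The spurious total indirect effect at p = 0.75 and r = 0.1 is 0.75 × 0.042 = 0.032 SD. The simulated mean in that cell is also 0.032. Across cells the simulated means are 0.022-0.032, 0.042-0.064 and 0.061-0.094 SD for r = 0.1, 0.2, 0.3, against 0.000-0.001 under ITT.

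**6. False mediation.** Simulation with no true effect: 10,000 trials per cell, 99 per arm, attendance correlated r with every mediator and with the outcome, total indirect effect, and a Monte Carlo 95% interval standing in for the bootstrap (largest simulation SE 0.4 points).

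| r | PP, 75% adherent | ITT | PP, 85% adherent | ITT |
|---|---|---|---|---|
| 0 | 4.7% | 5.0% | 4.6% | 4.8% |
| 0.1 | 6.3% | 4.9% | 5.6% | 4.9% |
| 0.2 | 10.0% | 4.9% | 7.1% | 4.5% |
| 0.3 | 16.7% | 4.8% | 10.1% | 4.8% |

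With r = -0.1, -0.2, -0.3 the per-protocol rates are 5.0-6.3%, 6.6-9.4% and 10.4-16.3%; at -0.2 and -0.3 nearly all errors point to SOM. Over all cells of both signs, ITT stays at 4.4-5.2%. With a single mediator, per-protocol gives 5.5-6.6%, 6.7-9.0% and 8.4-13.1% for r = 0.1, 0.2, 0.3.

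**The case against.** **The text.** If the blanket ITT sentence covers mediation, an ITT run is already promised; if it does not, there is no contradiction. Either way the repair is one sentence. But the SAP describes no ITT mediation, so the reader cannot rely on one.

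**The question.** A mechanism question arguably concerns people who received the training. ITT dilutes the indirect effect, and the mediator-to-outcome path is not randomized under ITT either. Both points stand: ITT protects the group-to-mediator and total-effect paths only. They justify keeping a per-protocol analysis, but not having it alone.

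**A safeguard exists.** The mixed models in Section 6 (*Course to treatment effect at T4*) cover these outcomes at T2 and, under the general rule, are ITT, so a null effect on outcome would be visible. This is partial protection, because no ITT analysis of the mediators is listed.

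**The illustration is generous.** The inputs are assumed, and change scores remove stable differences in level between attenders and others. For each mediator's own indirect effect within the three-mediator model, per-protocol error is lower: 5.1-5.7%, 5.8-7.7% and 8.1-12.1% at r = 0.1, 0.2, 0.3, against 4.6-5.1% under ITT. This tempers the size but not the direction.

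**ITT needs data from non-attenders.** This also stands. If half of them lack T1/T2 scores, complete-case ITT error is 4.8-5.1%, 5.1-6.1% and 6.0-7.0% at r = ±0.1, ±0.2, ±0.3, still below per-protocol in each of these cells. If most lack them, complete-case ITT approaches the per-protocol set.

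**Conclusion.** The concern holds. As written, II.5 is answered only from a comparison in which one arm is selected after randomization, against the SAP's own general rule. The consequence cannot be sized from the SAP. Under the assumptions shown, it is near nominal when attendance is weakly related to untreated change. From a correlation of about 0.2 it is material for the total indirect effect, and less so for single mediators, particularly at 85% adherence. The finding assumes that all SOM participants stay in the set; if that is not intended, the set is undefined for one arm and still needs correcting. It concerns one explanatory secondary question and leaves the primary ITT result untouched. The change should be made, but it does not threaten the trial's main conclusion.

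**What to change.** - **Section 6, *Mediation of the effect*:** make ITT the main set, with the same mediators (T0-T1 change) and outcomes (T0-T2 change), and keep the per-protocol mediation as a labelled supplement.
- **Per-protocol definition:** state in one sentence that all SOM + SAU participants enter the set, or give a rule based on the T1/T2 practice question.
- **Missing T1/T2 scores:** state the method for the ITT mediation, for example multiple imputation by arm with a complete-case run beside it. The REML statement covers the mixed models only, and the *Missing data* section names no method for these scores.
- **Section 4, *Analysis populations*:** name any analysis that is not ITT.

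**Cost.** SAP wording, a missing-data step, and one further mediation model per listed outcome on data already collected: seven outcomes, or five if the three PHQ-SADS scales are combined.

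**Downside.** ITT is diluted by non-attenders. With an assumed true effect of 0.4 SD on each mediator in attenders only and no selection, the indirect effect is 0.75 × 0.4 = 0.30. Under ITT it falls to 0.30 × 0.75 = 0.225 (about 0.23) or 0.30 × 0.85 = 0.255 (about 0.26). Simulated power (3,000 trials per cell) falls from 88.1% to 70.8% with 75% adherent and from 90.3% to 81.7% with 85% adherent. Reporting both sets lets the reader weigh this loss against the selection.
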